3. SUMMARY/SYNOPSIS

Short Title	MODET			
Method	Multi-site prospective observational study			
Research Sites	Major Trauma Centres (MTC) within the Pan-London Major Trauma System: Royal London Hospital, Barts Health NHS Trust St Marys Hospital, Imperial College Healthcare NHS Trust Kings College Hospital, King's College Hospital NHS Foundation Trust St Georges Hospital, St George's University Hospitals NHS Foundation Trust			
Objectives/Aims	This study aims to: Identify the prevalence, severity and patterns of multiple organ dysfunction syndrome (MODS) Determine predictors and risk factors of developing MODS Identify age related characteristics that contribute to MODS Examine the mode of mortality associated with MODS Analyse the relationship between MODS and longer-term recovery and quality of life			
Number of	1346			
Participants/Patients				
Main Inclusion Criteria	Inclusion criteria: Adult patients (≥16 years of age) with multiple injuries admitted to adult critical care unit within the four London MTCs.			
Statistical Methods and Analysis	 Analysis populations: Patients who are greater than 64 years of age will comprise the older-age cohort and younger patients (controls) are defined as ≤64 years. Primary outcome analysis: Difference in proportion will be examined with chi squared or fishers exact tests. Secondary outcome analysis: Univariate analysis of variables between the two age groups will be conducted using unpaired students t-tests or Mann Whitney U tests. Analysis of more than two groups or variables will be conducted using ANOVA or Kruskal Wallis tests. 			
Proposed Start Date	1 st February 2017			
Proposed End Date	1 st May 2020			
Study Duration	Three years			

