4. INTRODUCTION

For the first time there are 11 million people aged 65 or over in the UK¹. The number of older people suffering traumatic injury is increasing ²⁻⁶. In those who survive the initial period after injury a significant proportion goes onto develop adverse events such as multiple organ dysfunction (MODS) ^{7,8}. This occurs as a result of an exaggerated systemic inflammatory response following major tissue trauma⁹, where one or more organs do not function as they did prior to the traumatic injury. Recent reports suggest that MODS affects up to 33% of trauma patients ^{7,10-12}. Younger injured people who develop MODS usually recover quickly¹³, whereas older patients appear to suffer prolonged organ dysfunction, which is complicated by persistent immunosuppression and infectious episodes^{10,14,15}. This extends hospital stay, increases resource use and delays recovery after trauma ^{11,12}. MODS in older people is also associated with increased mortality ¹⁶⁻¹⁸ characterised by late, indolent death ^{14,19}. International evidence suggests that older age is strongly associated with MODS after trauma ^{7,11,12,14}, however the age-related characteristics that contribute to this burden in the UK have not been reported.

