Paper CRFs will be stored within a locked office in each centre (only accessible to the centre PI and data collectors) and then entered onto the password protected study website by QMUL research nurses.

A password protected coding log which will include identifiable patient data (name, address and date of birth) for patients who have consented to long term outcome follow-up. This will be transferred to [name] (CI) at the end of the in-hospital data collection period. At ten months after injury the NHS Health and Social Care Information Centre (NHS Spine) or patients General Practitioner (GP) will be contacted to ensure that the patient is still alive at this time point. This will avoid erroneous long term follow up and exposing relatives to undue distress. At 12 months post injury, the EQ5D and questionnaire will be administered to each participant who has provided informed consent.

	In critical care	At discharge from hospital	10 month post injury NHS spine check/GP check	12 months post injury
Enrolment	х			
CRF initiation	х			
Informed	х			
consent				
Daily SOFA score	х			
and outcomes				
recorded				
CRF completion		х		
Long term			х	х
follow up				

Schedule of Assessment

End of Study Definition

The study will be formally completed when 12 month follow up for all patients has been obtained and data analysis is complete.

Sample size:

We are planning a study of older patients (≥65 years) and younger (<65 years) controls. Prior research data suggest that the MODS rate among younger patients is 23% and for older patients is 33%. If the true MODS rate in older people is 0.33, we will need to include 259 older subjects and 414 younger subjects per year to be able to reject the null hypothesis that the prevalence of MODS for older and younger patients is equal (power 0.80, alpha 0.05). The total sample size for the two year period is 1346 (518 older patients and 828 younger controls). Each London MTC will aim to enroll:

130 older patients (>64 years) and 207 younger patients (<65 years).

Methods of analysis:

Statistical analysis will be performed using SPSS v.23 (IBM Corporation, Armonk, NY,USA). A p value of <0.05 is considered statistically significant for univariate analysis. De-identified data will be cleaned and categorical data formatted into binary fields for analysis. Normal distribution will be assessed with the Shapiro-Wilk test.

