Univariate analysis of variables between the two age groups (< 65 years and ≥65 years) will be conducted using unpaired students t-tests or Mann Whitney U tests (for parametric and non-parametric data respectively). Analysis of more than two groups (for example thresholds of immune counts or degrees of organ dysfunction) will be conducted using ANOVA or Kruskal Wallis tests. Chi-squared statistic or Fisher's exact tests will be used to compare proportions of MODS between the two cohorts.

Multivariable regression analysis will be used to determine statistically independent relationships between MODS and age plus other significant independent variables (such as the effect of injury severity, blood transfusion, on the development of MODS). Multivariate linear regression will be used to analyse continuous dependent variables and binary logistic regression for binary dependent variables. Results of linear regression will be reported as Beta co-efficient with 95% confidence intervals, and for logistic regression adjusted Odds ratios (OR) with 95% confidence intervals.

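### The adjusted analysis of continuous secondary outcomes names plain linear regression with no allowance for unequal spread, so its 95% intervals may be too narrow or too wide; robust intervals would remove the doubt (minor)

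*Protocol*

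**What the plan says.** Under Methods of analysis in section 6, the protocol sets out two steps for continuous variables.

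- **Unadjusted.** The two age groups are compared with Student's t-test for parametric data and Mann-Whitney for non-parametric data. The synopsis (section 3) names the same pair: "conducted using unpaired students t-tests or Mann Whitney U tests". The only assumption check named is Shapiro-Wilk, which concerns normality and not variance.
- **Adjusted.** "Multivariate linear regression will be used to analyse continuous dependent variables", and "Results of linear regression will be reported as Beta co-efficient with 95% confidence intervals". No variance estimator, transformation or alternative model is named.

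The planned groups are unequal: "The total sample size for the two year period is 1346 (518 older patients and 828 younger controls").

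Section 5 lists critical care stay, total length of stay and one-year quality of life among the outcomes. Section 6 adds days on organ support, and EQ5D at 12 months. The protocol gives no standard deviation for any of them.

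**The concern.** Student's t-test and ordinary least squares both estimate one residual variance and apply it to both groups. With equal group sizes, unequal variances do little harm. With unequal sizes the pooled standard error is biased: too small if the smaller group is the more variable, too large if it is the less variable. The bias depends on the ratio of the group sizes, so recruiting more patients does not cure it.

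Day counts cannot fall below zero and usually have a long right tail, and EQ5D has a ceiling. In such outcomes spread tends to change with the mean, so equal variance across age groups is not a safe default. The unadjusted step makes some provision for awkward distributions. The adjusted step, which produces the coefficients and intervals that will be reported, makes none. At stake is whether those 95% intervals have the coverage they claim.

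**Working it through.** **Inputs from the protocol (section 6, Sample size).** 518 older and 828 younger patients; MODS rates of 33% and 23%; power 0.80; alpha 0.05. Sidedness is not stated, and two-sided is assumed.

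**Reproducing the plan's own figure.** With r = 414/259 = 1.598, p₁ = 0.33, p₂ = 0.23 and p̄ = (0.33 + 1.598 × 0.23)/2.598 = 0.2685:

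n(older) = [1.96·√((1 + 1/r)·p̄(1 − p̄)) + 0.8416·√(p₁(1 − p₁) + p₂(1 − p₂)/r)]² / (p₁ − p₂)² = (1.108 + 0.485)² / 0.01 ≈ 254

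This gives 407 younger patients. The stated 259 and 414 per year are within 3% of this, with power 0.808. Doubling gives 518 + 828 = 1346. The 1:1.6 imbalance is therefore a planned feature.

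**Assumption.** k is the older-to-younger SD ratio. The documents do not give it, so a range is shown. For regression, age is assumed to enter as the two-group indicator and the fit to be ordinary least squares.

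**Formulas (younger SD set to 1).**

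- True variance of the difference: k²/518 + 1/828
- Pooled variance: [(517k² + 827)/1344] × (1/518 + 1/828)
- R = √(pooled/true)
- True error at nominal 5% = 2 × (1 − Φ(1.96R)); coverage is its complement

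**Worked case, k = 1.5.** Pooled = (1990.25/1344) × 0.003138 = 0.004647. True = 0.004344 + 0.001208 = 0.005551. R = √0.837 = 0.915. Error = 2 × (1 − Φ(1.793)) = 7.3%.

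| k | R | True error | 95% interval coverage |
|---|---|---|---|
| 0.5 | 1.149 | 2.4% | 97.6% |
| 0.8 | 1.052 | 3.9% | 96.1% |
| 1.0 | 1.000 | 5.0% | 95.0% |
| 1.1 | 0.978 | 5.5% | 94.5% |
| 1.25 | 0.951 | 6.2% | 93.8% |
| 1.5 | 0.915 | 7.3% | 92.7% |
| 2.0 | 0.870 | 8.8% | 91.2% |

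Repeating this at 259 and 414 gives the same error rates to within 0.0001, which confirms that the size ratio matters and not the total.

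**Check by simulation with normal errors.** True error at nominal 5%:

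| k | Student's t | Welch's t | Least squares, one covariate | Same model, HC3 |
|---|---|---|---|---|
| 0.67 | 3.3% | 5.0% | 2.9% | 4.7% |
| 1.25 | 6.1% | 4.9% | 6.3% | 4.8% |
| 1.5 | 7.6% | 5.1% | 7.2% | 4.8% |
| 2.0 | 8.5% | 4.8% | 8.1% | 4.6% |

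Welch's test and HC3 errors hold the level in both directions.

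**The case against.** Five points can be made against this, and most of them limit it.

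1. **Direction.** A reader might infer that the protocol's rationale implies more spread in the older, smaller group, so that results are too optimistic. The Introduction says "whereas older patients appear to suffer prolonged organ dysfunction", and the planning rates differ: "Prior research data suggest that the MODS rate among younger patients is 23% and for older patients is 33"%. If MODS adds the same d days in both groups, the variance from the MODS/no-MODS mix alone is 0.33 × 0.67 × d² = 0.221d² against 0.23 × 0.77 × d² = 0.177d², an SD ratio of 1.12. But the Introduction describes duration of dysfunction in patients who develop MODS, not the spread of stay across a whole age group. It also reports higher mortality in older people with MODS, and death can shorten stay. The direction is not established.
2. **The t-test.** Variables judged non-normal go to Mann-Whitney. At this sample size Shapiro-Wilk detects even mild skew (96.5% rejection for a gamma variable of shape 20 at n = 518), so stays and day counts would rarely reach the t-test. This stands, and it leaves regression as the main issue. Mann-Whitney is itself not immune (6.4% and 7.2% error at k = 1.5 and 2), and Welch's test does not change that.
3. **Reading the model as ordinary least squares.** The protocol does not use that term, and an unseen statistical analysis plan may specify robust errors. That is fair. It is nonetheless the usual reading of linear regression named without qualification, and the contrast with the unadjusted step is in the protocol's own text.
4. **Coding of age.** The figures apply only if age enters as the two-group indicator. The protocol does not say so for the models.
5. **Reach.** The primary comparison uses chi-squared or Fisher's exact test, and binary outcomes use logistic regression. Neither is touched.

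**Conclusion.** The point holds as a minor recommendation on continuous secondary outcomes. The protocol names a method whose intervals may not have their stated coverage, and a better one is available at almost no cost. For SD ratios from 1.25 to 2, coverage falls to between 93.8% and 91.2%. At 1.1 the effect is trivial (94.5%). At ratios below 1 the intervals are too wide and power is lost. These sizes rest on assumed SD ratios, on ordinary least squares, on a two-group age term and on the planned 518 and 828.

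The documents do not support the stronger statement that the 5% level and 95% intervals fail for every continuous outcome: no standard deviation is given, and with equal variances the level is exactly 5%. Nor do they show that the error favours finding an age effect.

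**What to change.** In section 6, Methods of analysis, add one sentence stating that 95% confidence intervals and p-values from linear regression will use heteroscedasticity-robust (HC3) standard errors or a bootstrap. If the bootstrap is chosen, resample whole patients, because resampling residuals would bring the common-variance assumption back in. Apply this to all linear models and do not make it depend on a preliminary variance test.

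In section 6 and in the synopsis, replace Student's t-test with Welch's t-test for variables judged normal.

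The cost is two small text changes and a negligible loss of power if the variances are equal. The study team should confirm that the software named in the protocol (SPSS v.23) offers the chosen option. If the statistical analysis plan already specifies robust or bootstrap intervals, the protocol need only agree with it.

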9. ETHICS

This study will be carried out in accordance with the ethical Principals in the Research Governance Framework for Health and Social Care, Second Edition, 2005 and its subsequent amendments as applicable and applicable legal and regulatory requirements. The study has been reviewed and approved by the London South East Research Ethics Committee on 26th October 2016.

Each participant in the study will be approach for informed consent to allow non-clinical care staff (QMUL research nurses and Chief Investigator) to:

- 1. access the status of the participant at ten months post injury via NHS Health and Social Care Information Centre or the patients GP
- 2. follow up the participant via telephone, letter or email at 12 months post injury

Incapacity:

For most of the severely injured patients admitted to a critical care unit, there will be a period of time where they require sedation and ventilation (life support) resulting in temporary incapacity. Specific injury factors such as hypoxia, haemorrhage or the presence of a traumatic brain injury may also add to the incapacity. During the in-hospital stage of the study, all of the data being collected is part of routine clinical care therefore there is time to wait to see if the patient regains capacity. Once this occurs, the study can be explained by the local collaborator and a participant information sheet given to the patient for 24-48 hours prior to seeking informed consent.

In those patients where capacity is not regained during the critical care stay every effort will be made to identify and consult with someone who knows the person who lacks capacity, such as a relative or significant other next-of-kin. The study will be explained to the personal consultee. This individual will be provided with a personal consultee written information sheet prior to seeking consent on a personal consultee consent form.

Where the person who lacks capacity has no family or friends who are willing and able to fulfil this role the local collaborator will ask the patients critical care consultant to provide consent as a nominated consultee.

Patients who die during the in-hospital study period will have their de-identified data included in the study.

10. DATA HANDLING AND RECORD KEEPING:

Routine de-identified clinical data will be collected and stored as per local Trust policies in accordance with the Data Protection Act and NHS Caldicott Guardian. When the study is complete, the Principal Investigator will ensure that records are to be stored for 20 years as per the Sponsors Research Governance Framework and Trust Policy in the approved repository for long-term storage of local records is the Trust Modern Records Centre.

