5. STUDY OBJECTIVES

This study aims to:

- Identify the prevalence, severity and patterns of MODS in older patients
- Determine predictors and risk factors of developing MODS for older patients
- Identify age related characteristics that contribute to MODS
- Examine the mode of mortality associated with MODS
- Analyse the relationship between MODS and longer-term recovery and quality of life for older patients

The primary outcome is the presence of MODS during the critical care admission period. An individual Sequential Organ Failure Assessment (SOFA) score of 1 in any organ represents dysfunction. Multiple organ dysfunction syndrome (MODS) is defined as a total daily SOFA score of >5.

Secondary outcomes are in-hospital mortality, ventilator use, level of organ support, adverse events such as infection or stroke, critical care stay and total length of stay. Longer terms outcomes are quality of life and recovery at one year post injury.

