6. METHODOLOGY

Study Design

This is a pan-London prospective observational study which aims to characterise organ dysfunction in older trauma patients \geq 65 years. All adults admitted to an adult critical care unit within one the London Major Trauma Centres (MTCs) will be considered for enrolment, with younger patients (<65 years) recruited as a control group.

Settings

There are four MTCs in London. Each site will have a nominated Principal Investigator (PI). Organ injury scoring training will be provided for local research nurses or data collectors prior to study commencement. Two funded research nurses from Queen Mary University of London (QMUL) will support patient enrolment, data collection and data quality monitoring across the four MTCs. Each site will be supported by an on-line information folder with the protocol, guidance/explanatory notes and contact details of the Principal Investigator. For this study, a critical care unit is defined as either an Intensive Care Unit (Level 3 care) or a combined unit of Intensive Care (Level 3 care) and High Dependency Unit (Level 2 care).

Inclusion Criteria

- Adult major trauma patients (≥16 years of age) admitted to adult critical care within one of the four London Trauma System MTCs. This includes direct admissions from the Emergency Department, admissions from the operating theatre or from a ward, transfers from other facilities and readmission to critical care.

Exclusion Criteria

- Patients with a burns-only injury
- Patients who are prisoners
- Patients who decline to provide informed consent or do not have consultee consent

Study Design / Plan – Study Visits

Trauma patients (≥16 years of age) admitted to MTC critical care during the enrolment phase of the study (two years in total) will be identified by the local PI together with clinical care staff. The local PI will be responsible for ensuring patient enrolment, participant consent, data collection, patient detail de-identification, data entry and storage. Data from routine clinical care records will be recorded daily by local and QMUL research nurses whilst the patient is admitted to the critical care unit.

The clinical data collection will include:

- Demographics: Age within a range, gender, co-morbid disease, pre-injury medication
- Injury variables: Mechanism of injury, Injury Severity Score (ISS)
- Organ dysfunction: The frequency, pattern and severity will be measured daily using Sequential Organ Failure Assessment (SOFA) scoring

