- Total number of days on organ support (CTCOFR score)
- Immune cell function: Daily clinical measures of lymphocyte and neutrophil counts
- Adverse events: Such as infection, delirium, stroke or cardiac dysfunction
- Nutrition: Nutritional requirements, nutrition intake and weight measurements
- Frailty screening using the Edmonton Frail Scale (https://www.nscphealth.co.uk/edmontonscale-pdf)
- Length of stay: In critical care and total hospital stay
- Mortality: Mode and timing

[figure not shown]
As soon as clinically appropriate (determined by the clinical care team in charge of the patient), consent will be sought for inclusion of data into the study and long term follow up. If the patient remains incapacitated due to injury or treatment, consent will be sought from a personal or nominated consultee.

At 12 months post injury patients will be approached by letter, email or telephone (according to patient wishes) and health-related quality of life and longer-term recovery data will be collected using the EuroQol-5D (EQ5D) questionnaire. This was chosen as it has been previously validated to capture outcomes in trauma patients including older people and takes approximately 15 minutes to complete.

Study Scheme Diagram

Each MTC will be identified by a number rather than name.

Eligible trauma patients admitted to the critical care unit during the study period will be identified by the clinical care team.

The PI and research nurses have responsibility to ensure patient anonymity is protected and maintained. They will also ensure that patient identities are protected from any unauthorised parties. Information regarding study patients will be kept confidential and managed in accordance with the Data Protection Act, NHS Caldicott Guardian, The Research Governance Framework for Health and Social Care and Research Ethics Committee Approval.

Although patient identifiable data will be available to research staff they will not be entering it on to the paper case record form (CRF). The de-identified data required for this study is already recorded as part of routine clinical care and as part of the Intensive Care National Audit and Research Centre (ICNARC) audit. Organ failure scoring is not usually conducted as part of routine clinical care however it uses parameters that are recorded by critical care clinical staff on a daily basis.

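### The protocol contradicts itself on whether consent governs in-hospital data; if it does, inclusion depends on survival and in-hospital mortality is overstated

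*Protocol*

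**What the plan says.** Three parts of the Protocol bear on who is in the data set.

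- Section 6, Exclusion Criteria, removes this group: "Patients who decline to provide informed consent or do not have consultee consent". It states no exception for patients who die.
- Section 6, on study visits, says that once clinically appropriate, "consent will be sought for inclusion of data into the study and long term follow up". On this wording consent covers the in-hospital data as well as follow-up.
- Section 9 describes a narrower consent: "Each participant in the study will be approach for informed consent to allow non-clinical care staff" to do two things, namely check status at ten months and make contact at twelve months. In-hospital data are not on that list.

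Under Incapacity, section 9 describes in-hospital data as part of routine care, "therefore there is time to wait to see if the patient regains capacity". Patients who stay incapacitated go to a personal consultee. If there is none, the local collaborator will "ask the patients critical care consultant to provide consent as a nominated consultee". The section ends with the rule on deaths: "Patients who die during the in-hospital study period will have their de-identified data included in the study".

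The outcomes affected are in section 5: "The primary outcome is the presence of MODS during the critical care admission period", and "Secondary outcomes are in-hospital mortality, ventilator use, level of organ support" among others.

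**The concern.** Because consent is deferred until capacity returns, death can come before any consent decision. On the section 6 reading, a survivor who refuses, or who is never successfully consented, drops out, while a patient who dies stays in. Inclusion then depends on survival, which is itself a secondary outcome. Section 4 also links survival to the primary outcome, since it reports higher mortality with MODS in older people. A larger sample does not remove such a bias.

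The contradiction is also a practical problem. A site cannot tell whether a survivor who refuses follow-up keeps or loses the in-hospital record, and no rule covers a patient who declined, or whose consultee declined, and then died. Four centres could build four different denominators. A statistical analysis plan could describe an adjustment, but it cannot decide who is enrolled or recover counts that were never logged.

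**Working it through.** **Inputs from the Protocol.** MODS 33% in older and 23% in younger patients, power 0.80, alpha 0.05, 259 older and 414 younger per year, 518 and 828 over two years (section 6, Sample size). The sample size reproduces: a two-sided comparison of 33% v 23% at ratio 414/259, pooled variance, no continuity correction, needs 254 and 406, within 3% of the stated figures. It does not depend on this point; 33% and 23% serve below as true values.

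**Assumed inputs.** The Protocol gives no survivor consent rate (c) and no death risks. Both are varied below. Deaths are taken to be always included.

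**Mortality.** With true mortality D, observed mortality = D / [D + (1 − D)c]. This exceeds D whenever c < 1. For D = 15%:

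- c = 0.9: 0.15 / (0.15 + 0.765) = 16.4%
- c = 0.8: 0.15 / (0.15 + 0.680) = 18.1%
- c = 0.7: 0.15 / (0.15 + 0.595) = 20.1%

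**MODS prevalence.** Let m be true prevalence, and dM and dN the death risks with and without MODS. Then

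observed MODS = m[dM + (1 − dM)c] / {m[dM + (1 − dM)c] + (1 − m)[dN + (1 − dN)c]}.

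Example, older patients, dM = 40%, dN = 10%, c = 0.7: 0.33 × 0.82 = 0.2706; 0.67 × 0.73 = 0.4891; 0.2706 / 0.7597 = 35.6%.

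| Assumed death risk with/without MODS | Assumed survivor consent | Older MODS | Younger MODS | Difference (points) |
|---|---|---|---|---|
| any | 100% | 33.0% | 23.0% | 10.0 |
| older 40/10%, younger 20/3% | 90% | 33.7% | 23.3% | 10.4 |
| same | 80% | 34.6% | 23.7% | 10.8 |
| same | 70% | 35.6% | 24.3% | 11.4 |
| 15/15% in both (no link) | 70% | 33.0% | 23.0% | 10.0 |
| 25/5% in both | 70% | 34.8% | 24.5% | 10.3 |
| older 30/20%, younger 30/3% | 70% | 33.9% | 25.0% | 8.9 |
| older 40/10%, younger 20/3% | older 90%, younger 70% | 33.7% | 24.3% | 9.5 |
| same | older 70%, younger 90% | 35.6% | 23.3% | 12.3 |
| same | with MODS 70%, without 90% | 30.7% | 20.1% | 10.7 |

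Differences are taken before rounding. The true odds ratio is 1.65. It stays at 1.65 with 25/5% in both groups and falls to 1.54 with 30/20% v 30/3%.

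**False positives.** If true MODS is 27% in both groups, with death risks 40/10% and 20/3% and 518 v 828 patients, the two-sided rejection rate is 5.1%, 5.6% and 6.7% at 90%, 80% and 70% consent.

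**What weighting does.** Weighting consenting survivors by 1/c restores mortality: at c = 0.7, 0.15 / (0.15 + 0.595/0.7) = 15%. It does not repair MODS prevalence when consent depends on MODS. In the last table row, older survivors are 0.198 with MODS and 0.603 without. Those consenting are 0.1386 + 0.5427 = 0.6813 of 0.801, a rate of 0.851. Weighted MODS is 0.132 + 0.1386/0.851 = 29.5%, against 30.7% unweighted and 33% true.

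**The case against.** The strongest reply is that one reading removes the selection altogether. Section 9 ties consent to later contact only and treats in-hospital data as routine. Section 6 keeps its coding log for those who consented to long-term follow-up and sends the questionnaire to participants who gave consent, which suggests that some participants did not. This stands as a possible reading, but the exclusion criterion and the consent wording in section 6 say otherwise, so the conflict remains.

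A reader might infer that every death enters without consent. The sentence on deaths is silent on consent and on earlier refusals, and the exclusion criterion makes no exception for deaths. Inclusion of all deaths is therefore an inference.

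A reader might also infer that the age difference in MODS is inflated. That does not follow: under plausible inputs the gap rises, barely moves or falls. Overstated MODS prevalence is conditional too, since it reverses if survivors with MODS consent less often.

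The size may also be modest. The nominated-consultee route limits losses among survivors who stay incapacitated, leaving mainly refusals and survivors never successfully consented. The planned 518 v 828 gives a 95% half-width of 1.96 × √(0.33 × 0.67/518 + 0.23 × 0.77/828), about 5 points, against a shift of 0.4 points at 90% consent in the second table row. This limits the concern for the primary comparison but does not remove the mortality bias.

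**Conclusion.** The contradiction between sections 6 and 9 needs no assumption and should be resolved. On the section 6 reading, with deaths included regardless, overstatement of in-hospital mortality follows from the rule for any survivor consent below 100%. On an assumed true 15% it is 1.4, 3.1 and 5.1 points at 90%, 80% and 70% consent.

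MODS prevalence is probably overstated, given the link between MODS and death in section 4, provided survivor consent is unrelated to MODS. The direction of any bias in the age comparison is not determined. With 70% consent in both age groups, the assumed death risks moved a true 10.0 points to between 8.9 and 11.4; unequal consent by age gave 9.5 to 12.3. None of these sizes can be derived from the document. All are small if consent is near 90%. The point is a firm one for mortality and for the inclusion rule, and a caution for the primary outcome.

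**What to change.** 1. Reconcile the exclusion criterion and consent wording in section 6 with the consent list and the sentence on deaths in section 9, so that one stated rule governs in-hospital data whatever the vital status. State what happens to patients who declined, or whose consultee declined, before dying. The rule should not drop patients who die before consent can be sought, because that would bias mortality downward.
2. If survivors' in-hospital data do need consent, have each centre log anonymous counts of eligible, consented, declined and died by age group.
3. In that case, report mortality, MODS prevalence and the age comparison with consenting survivors weighted by eligible/consenting survivors within centre and age group, alongside the unweighted results.

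The cost is a change of protocol and ethics-committee wording, a count-only log of patients whom the sites already identify, and a weighting step. Intervals become slightly wider. The weighting assumes that consent is unrelated to MODS and severity among survivors within each cell. This should be stated as a limitation, since where it fails the weighted MODS prevalence can be further from the truth than the unweighted one.
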